# 8. RESEARCH QUESTION AND OBJECTIVES

The objective of this study is to characterize risk factors for myocarditis in the following three cohorts: 1) myocarditis diagnosed post any type of mRNA COVID-19 vaccine, 2) myocarditis diagnosed post SARS-CoV-2 infection (2020-2022), or 3) myocarditis diagnosed prior to the COVID-19 era (pre-2020). To accomplish this objective, the study will characterize demographics, medical history, and comorbidities of patients with myocarditis prior to diagnosis during a baseline period and then examine risk factors for myocarditis using multivariable models. Myocarditis cases identified in the EHR or claims post-vaccine or post COVID-19 infection, as well as a sample of cases in the pre COVID era cohort, will be validated by clinicians using the Brighton Collaboration criteria  applied to review of medical records at Optum as the gold standard. Using those validated cases, the study will also assess and compare the PPV for the myocarditis definitions based on codes for the three cohorts in the Optum deidentified EHR data.

Among patients diagnosed with myocarditis in the deidentified Optum EHR data, the study specific objectives are detailed below.

## **Research question:**

What are the risk factors for myocarditis among the following three cohorts? 1) Myocarditis after mRNA COVID-19 vaccine, 2) Myocarditis after SARS-CoV-2 infection (2020-2022), or 3) Acute/viral myocarditis prior to the COVID-19 era (pre-2020).

# Primary objective:

1. To assess and compare demographic, medical history, and comorbidities that may be risk factors for myocarditis in each of three cohorts: 1) Myocarditis after mRNA COVID-19 vaccine, 2) Myocarditis after SARS-CoV-2 infection (2020-2022), or 3) Acute/viral myocarditis prior to the COVID-19 era (pre-2020).

#### **Secondary objectives:**

- 1. To examine the risk factors in each myocarditis cohort stratified by age group at diagnosis, sex, time period and follow-up time (years).
- 2. To assess and compare the validity of myocarditis diagnosis case definitions in administrative data for each cohort, via calculating the PPV using electronic medical record review.

#### 9. RESEARCH METHODS

#### 9.1. Study design

This is a NI, observational, retrospective cohort study utilizing a nested case-control design with secondary data collection. The broader cohort for this study is the Optum EHR database during the proposed study period of 01 January 2010 to most recent available at the time of start of data

[figure not shown]
collection (31 March 2023). This study period has been chosen to reflect the most current and complete data in the Optum database, with sufficient baseline time to examine risk factors for patients with myocarditis in each of the cohorts with index dates of 2016-later.

**Figure 1** summarizes the overall study design. Among the overall Optum EHR study population, the following mutually exclusive cohorts and index dates will be defined to address the study objectives:

- Cohort 1 Post-mRNA COVID-19 vaccination myocarditis cohort: first date of a
  myocarditis diagnosis code within 21 days after vaccination from 11 December 2020 to most
  recent data available, allowing for at least 30 days pre or post index myocarditis diagnosis for
  medical notes to confirm diagnosis through end of study period.
- Cohort 2 Post-SARS-CoV-2 infection myocarditis: first date of a myocarditis diagnosis code within 8 weeks after a positive SARS-CoV-2 test from 01 January 2020 to most recent data available, allowing for at least 30 days pre or post index myocarditis diagnosis for medical notes to confirm diagnosis through end of study period.
- Cohort 3 Pre-COVID myocarditis: most recent date of a myocarditis diagnosis from 01 January 2016 to 01 November 2019, allowing for at least 30 days pre or post index myocarditis diagnosis for medical notes to confirm diagnosis through end of study period.
- Controls for the multivariable risk factor analysis, a random sample of matched patients
  without myocarditis will be selected, e.g. with an encounter date within the same month as
  the index date for the myocarditis case, and with a similar amount of follow-up time from
  entry into the cohort and activity in the database. Additional matching criteria may be
  determined, and details of the matching methods and appropriate modeling considerations
  will be provided in the SAP.

Additional details on index dates and episode definitions will be provided in the SAP.

Figure 1. Study Design

- Censored at minimum of myocarditis diagnosis, death, disenrollment, or end of the study period
- Controls risk-set matched on e.g. month/year of cohort entry, duration of follow up (from cohort entry), integrated delivery network (IDN). Matching criteria will be detailed in the SAP.
- Timeframe for each myocarditis sub-cohort:
  - 1) Post-vaccination myocarditis: December 11, 2020 November 01, 2022
  - 2) Post-SARS-CoV-2 myocarditis: January 01, 2020 November 01, 2022
  - 3) Pre-COVID era myocarditis: January 01, 2016 November 01, 2019

## 9.2. Setting

This study will use the US-based Optum's deidentified Electronic Health Record (EHR) data, with supplemental linkage to Optum's Integrated Claims-Clinical adjudicated claims dataset for those patients in the EHR who also have claims data available. For a subset of patients in the EHR, data exist including patient electronic clinical notes which will allow manual clinician review at Optum to confirm myocarditis cases based on available data that align with the Brighton Collaboration criteria. Review of clinical notes will not be conducted for the random sample of patients without evidence of myocarditis that will serve as controls for the risk factor analysis. Optum's role, processes, and data is described in more detail in Section 9.4.

#### 9.2.1. Inclusion criteria

Patients must meet all of the following criteria to be eligible for inclusion in the study:

1. All ages

# **Myocarditis cases:**

- 2. Diagnosis of myocarditis identified using ICD codes in EHR and/or claims when available. (ICD codes will be provided in the SAP)
- 3. At least one myocarditis inpatient record or two myocarditis records of any type dated greater than or equal to 30 days apart
- 4. Myocarditis diagnosis date between 01 January 2016 most recent EHR data available (31 March 2023)
- 5. At least 365 days of enrollment or activity in the EHR prior to the index myocarditis diagnosis.

Myocarditis cases meeting the above criteria will be divided into the following three cohorts with their own unique inclusion criteria:

- a) Cohort 1 Post- mRNA COVID-19 vaccine myocarditis cases:
  - 1. Myocarditis diagnosis date 11 December 2020 or later
  - 2. Record of mRNA vaccination within 21 days prior to the myocarditis diagnosis without a record of SARS-CoV-2 positive test within 8 weeks prior to myocarditis diagnosis
  - 3. Availability of medical notes to use for confirmation of myocarditis post-mRNA COVID-19 vaccination thirty days before or after the index event
- b) Cohort 2 Post- SARS-CoV-2 infection myocarditis cases:
  - 1. Myocarditis diagnosis date 01 January 2020 or later
  - 2. Record of SARS-CoV-2 positive test within 8 weeks prior to myocarditis diagnosis, with no record of mRNA COVID-19 vaccination during that time
  - 3. Availability of medical notes to use for confirmation of myocarditis post-SARS-CoV-2 infection thirty days before or after the index event
- c) Cohort 3 Pre-COVID-19-era acute/viral myocarditis cases:
  - 1. Most recent Myocarditis diagnosis date prior to 01 November 2019
  - 2. Availability of medical notes to use for confirmation of myocarditis within thirty days before or after the index event

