#### 7. RATIONALE AND BACKGROUND

Myocarditis is an inflammatory disease of the myocardium diagnosed by established histological, immunological and immunohistochemical criteria. Clinically, myocarditis can present in a variety of ways, ranging from mild symptoms of chest pain and palpitations associated with transient Electrocardiogram (ECG) changes to life-threatening cardiogenic shock and ventricular arrhythmia . Myocarditis is a challenging diagnosis due to the heterogeneity of clinical presentations, and several classifications exist . During the COVID-19 era, diagnostic criteria have been based on those from the CDC and the Brighton Collaboration. The actual incidence of myocarditis is also difficult to determine as endomyocardial biopsy (EMB), the diagnostic gold standard, is used infrequently. It is estimated that approximatively 1.5 million individuals experience myocarditis per year worldwide, with the incidence varying from 1 to 40 per 100,000 depending upon the population characteristics. 

Although the aetiology of myocarditis often remains undetermined, a large variety of infectious agents, systemic diseases, drugs, and toxins can cause the disease. Molecular techniques suggest that viral infections are the most important cause of myocarditis in North America and Europe with genomes of enterovirus, adenovirus, influenza viruses, human herpes virus-6 (HHV-6), Epstein-Barr-virus, cytomegalovirus, hepatitis C virus, and parvovirus B19 reported in the myocardium of patients with myocarditis. In almost 50-80% of cases, no cause is ever found. 9

Outcome and prognosis of myocarditis depends on aetiology, clinical presentation, and disease stage. The fatality rate for myocarditis varies according to the methodology, geographic region, or time of the study, and generally converge to a rate of 5% myocarditis resulting in death in the short-term, and much higher if the acute episode required admission in intensive care or use of mechanical circulatory support, or if the myocarditis diagnosis was confirmed on histology. 10,11,12,13,14,15

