Myocarditis has been reported as an AE following immunization with COVID-19 mRNA vaccine. In aggregate, epidemiology studies reported higher risk after Dose 2 compared to Dose 1 , shorter duration between Dose 1 and Dose 2 , and among younger males compared to older males or females of any age post-vaccination, with the highest excess risk reported in young males being <1 case per 10,000 vaccine doses. The clinical course of post-vaccination myocarditis and pericarditis tends to be mild, responds to standard of care treatments and requires a relatively short duration of hospitalisation (2-4 days). Short-term data on mortality is reassuring, with some studies showing a lower mortality compared with myocarditis of other causes, and other studies finding statistically comparable rates. The prognosis is comparable with myocarditis of other causes. Apart from male gender, younger age, and second dose, no other risk factors were identified for post-vaccine myocarditis.

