For the validation process using the electronic clinical notes (which will be converted to deidentified structured data for analyses), the Optum Natural Language Programming (NLP) team will determine if clinical notes are available for all qualifying patients with post-vaccine myocarditis, all qualifying post-SARS-CoV-2 infection myocarditis, as well as random samples of myocarditis diagnosed pre-2020. Optum will perform a series of "enhanced search" queries on the patient notes to determine key term content. Next, the Optum NLP team will use the key terms to extract note snippets into a file for review by the Optum Clinical team. These notes snippets will then be used to validate myocarditis cases per the Brighton Collaboration Criteria that were identified in the EHR using the inclusion and exclusion criteria specified in Section 9.2. After clinical review of the notes involving two clinicians from Optum, and categorization of the content for analysis, the resulting table of criteria will be created. The myocarditis cases will then be classified as validated or not validated, and relevant information entered into a spreadsheet that will serve as the data collection tool. Finally, the Optum clinical review team will provide these results of the case validation to the Optum Health Economics and Outcomes Research (HEOR) analytics team, whose members will identify matched controls for each case and conduct the multivariable analyses to assess risk factors for myocarditis

 CFR 164.514(b)(1).

 Guidance Regarding Methods for De-identification of Protected Health Information in Accordance with the Health Information Insurance Portability and Accountability Act (HIPAA) Privacy Rule (Dated as 04 September 2012, as first released on 26 November 2012).

using the structured data. This information will also be used to calculate the PPV of the algorithm used to initially identify the myocarditis cases in the structured EHR database.

Data will be transferred from the clinical review team to Optum's HEOR team via standard Data Transfer API (application programming interface). Extraction, merging, and cleaning of EHR and NLP-rendered data will be performed and adjudicated by at least two HEOR programmers and two HEOR analysts/directors. All data steps and code locations are formally documented in a data dictionary and are reviewed by the directing analyst and researcher before commencement of programming.

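### For never-admitted patients in Cohorts 1 and 2, the rule of two records at least 30 days apart makes case status depend on events after the index date

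*Protocol*

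**What the plan says.** Protocol section 9.2.1, criterion 3 for myocarditis cases, requires "At least one myocarditis inpatient record or two myocarditis records of any type dated greater than or equal to 30 days apart". It applies to all three cohorts.

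The index date differs by cohort (section 9.1):

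- Cohort 1 takes the first "myocarditis diagnosis code within 21 days after vaccination from 11 December 2020 to most" recent data.
- Cohort 2 is defined as "Cohort 2 Post-SARS-CoV-2 infection myocarditis: first date of a myocarditis diagnosis code within 8 weeks after a positive SARS-CoV-2 test".
- Cohort 3 is defined as "Cohort 3 Pre-COVID myocarditis: most recent date of a myocarditis diagnosis from 01 January 2016 to 01 November 2019".

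Controls (section 9.2.1, controls for risk factor analysis) need an encounter in the case's index month, 365 days of earlier enrollment or activity, and no myocarditis before index. Apart from matching details left to the SAP, nothing is asked of them after index.

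On the clinical picture, section 7 says myocarditis presents in forms "ranging from mild symptoms of chest pain and palpitations associated with transient Electrocardiogram (ECG) changes to life-threatening cardiogenic shock" and worse. It says the post-vaccination form "tends to be mild, responds to standard of care treatments and requires a relatively short duration of hospitalisation (2-4 days").

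Section 9.6 plans clinician review of note snippets, subject to note availability, for all qualifying post-vaccine cases and "all qualifying post-SARS-CoV-2 infection myocarditis, as well as random samples of myocarditis diagnosed pre-2020".

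**The concern.** A patient seen only in an emergency department or clinic, and coded twice a week apart during one acute episode, is not a case. The same patient coded again five weeks later is. In Cohorts 1 and 2 the index is the first code in the window, so a new never-admitted episode becomes a case only through something that happens 30 or more days afterwards: the patient must be alive, still in a contributing network, and coded with myocarditis again.

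This is selection on post-index information for cases only. Anything that makes later recoding more likely, such as existing cardiac disease, heavier use of care or stable coverage, will be over-represented among the non-admitted cases. It can then appear as a risk factor for onset, which is what the primary objective sets out to estimate. The validation work cannot expose the problem, because PPV has only qualifying patients in its denominator.

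**Working it through.** **No plan figure to reproduce.** Section 9.5 gives feasibility counts only (about 240, 1,730 and 7,200) and does not say whether criterion 3 had been applied to them. The check is therefore of the rule's logic, then of its possible size.

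**Step 1: who is affected, by route and cohort.**

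| Patient | Cohorts 1 and 2 (index = first code in window) | Cohort 3 (index = most recent date) |
|---|---|---|
| Any inpatient record | Qualifies on that record | Qualifies on that record |
| Never admitted, new episode, second record 30 or more days after the first | Qualifies; second record is after index | Qualifies; the paired record normally precedes index |
| Never admitted, new episode, one record or all records within 30 days | Not a case | Not a case |

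The dependence on post-index events is thus specific to never-admitted new episodes in Cohorts 1 and 2. Criterion 3 also sets no maximum gap, and the case criteria state no myocarditis-free history. As written, an old code plus one outpatient code in the window could qualify, while two codes a week apart in a new episode do not.

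**Step 2: cut-off by the end of data.** Data end on 31 March 2023. A first non-inpatient code after 1 March 2023 (31 March minus 30 days) cannot be paired in time. If the Figure 1 closing date of 1 November 2022 applies, 150 days remain, so cut-off by the end of data matters little. Death, care elsewhere and no recoding remain.

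**Step 3: size of a spurious association.** Assumptions, none of them given in the protocol:

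- n = share of true cases with no inpatient record
- s = probability that a non-inpatient case has a record 30 or more days later
- the factor has no effect on onset or on admission, and controls represent the source population

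Probability that a true case qualifies = (1 − n) + n·s.

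Spurious OR = [(1 − n) + n·s₁] / [(1 − n) + n·s₀].

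With s₁ = 0.8 (factor present) and s₀ = 0.4 (factor absent):

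| n | Factor present | Factor absent | Spurious OR |
|---|---|---|---|
| 0.05 | 0.99 | 0.97 | 1.02 |
| 0.10 | 0.98 | 0.94 | 1.04 |
| 0.20 | 0.96 | 0.88 | 1.09 |
| 0.30 | 0.94 | 0.82 | 1.15 |
| 0.60 | 0.88 | 0.64 | 1.38 |

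Under these inputs the rule loses 1 − 0.4 = 60% of non-inpatient cases without the factor and 1 − 0.8 = 20% of those with it.

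Other assumed contrasts:

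- s from 0.3 to 0.6: 0.80/0.65 = 1.23 at n = 0.50, 0.92/0.86 = 1.07 at n = 0.20, 0.98/0.965 = 1.02 at n = 0.05.
- s from 0.2 to 0.8: 0.90/0.60 = 1.50, 0.96/0.84 = 1.14 and 0.99/0.96 = 1.03 at the same n.

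**Step 4: cases kept in Cohort 1**, treating 240 as the count before the rule (an assumption) and letting s run from 0.2 to 0.8. Kept = 240 × [(1 − n) + n·s]: 230 to 238 at n = 0.05, 202 to 230 at n = 0.20, 144 to 216 at n = 0.50.

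**Step 5: does another part of the plan recover the missed cases?** The subgroup by case definition in section 9.7 is built from the section 9.2.1 criteria, so a patient who fails criterion 3 is in none of its groups. Section 9.6 reviews qualifying patients only. Section 9.9 discusses misclassification, rule-out codes and care outside the network, but not the loss of never-admitted cases under this rule.

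**The case against.** The rule has a sound motive. Section 9.9 warns that codes may reflect a rule-out work-up or an old event, and repeat codes within days are what a work-up produces. Preferring specificity to sensitivity in a code algorithm is legitimate, particularly in Cohort 3, where only random samples are reviewed, and in the models that use code-identified cases without validation. This stands, and it is a reason not to replace the primary definition.

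Three stronger readings are tempting and are not supported:

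- A reader might infer that the rule removes the disease the protocol regards as typical after vaccination. The sentence in section 7 that calls it mild also gives it a hospital stay of 2 to 4 days, so that course enters by the inpatient route.
- A reader might infer that the rule removes a larger share of Cohort 1 than of the other cohorts, so that the bias is known not to cancel in the comparison. The protocol gives no inpatient share for any cohort, so neither the size nor the direction of such a difference can be shown.
- A reader might extend the argument to all cases. Cohort 3 is about 7,200 of 9,170 feasibility cases (79%), and its index is the most recent diagnosis date, so dependence on later persistence does not carry over in the same way.

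If nearly all cases are admitted, the bias is negligible, as the first rows of the table show. What the objection does not answer is the asymmetry itself: in Cohorts 1 and 2, non-admitted cases must meet a post-index condition that controls need not meet, and the excluded patients are never identified.

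**Conclusion.** The concern holds for never-admitted new episodes in Cohorts 1 and 2. Their case status depends on survival, network retention and recoding at least 30 days after index, so odds ratios for factors linked to these can be distorted, and PPV among qualifiers cannot show what was missed. Section 7's own range of presentations includes mild illness, so non-admitted disease is within the condition studied.

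The effect may be small or material: a spurious OR of about 1.02 with 5% of cases non-inpatient, 1.09 with 20% and 1.38 with 60%, under assumed recoding of 80% against 40%. Across all contrasts tried the range is 1.02 to 1.50. It turns mainly on the inpatient share, which the study can count but the protocol does not state. This warrants a second case definition. It does not invalidate the current one.

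**What to change.** - Keep criterion 3 as one case definition in all cohorts.
- For Cohorts 1 and 2, add a second definition that also accepts non-inpatient cases with no minimum 30-day gap when the Brighton note review confirms them. That review is already planned for all qualifying cases with notes in these cohorts and would be extended to the added candidates.
- Run the risk-factor models under both definitions and show the odds ratios together.
- Report case counts and PPV by qualifying route: inpatient record, two records at least 30 days apart, other non-inpatient. For the last route the PPV denominator should be all candidates reviewed, not only those confirmed.
- Do not require a later second record in Cohort 3. With the index at the most recent diagnosis date, such a pair would be almost impossible to meet.
- Name the loss of never-admitted cases as a limitation in section 9.9.

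Cost: amendment wording, a re-run of the case algorithm, matched controls for the added cases, somewhat more snippets for the same two clinicians, and a lower PPV under the broader definition, which the study would measure.

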## 9.7. Data analysis

# **Primary objective**

In primary analyses, descriptive statistics will be presented to characterize myocarditis patients in terms of demographic and clinical characteristics (including clinical characteristics of the myocarditis episode, as well as clinical history of the patient) as of the index date (date of myocarditis diagnosis code for myocarditis cases, or matched month/year among the control group). Specific demographics and clinical characteristics of interest are described in Section 9.3. Descriptive statistics will include counts and percentages for categorical data. For continuous variables, we will provide statistics such as mean, median, standard deviation, and range.

Additionally, appropriate statistical models such as conditional logistic regression or generalized estimating equations (GEE) incorporating non-independence of observations will be described in greater detail in the SAP. These models will estimate odds ratios (ORs) and 95% CIs of associations between demographics, clinical characteristics, and empirical model identified risk factors (based on either a stepwise selection approaches or via statistical significance in univariate models) and myocarditis. Models may incorporate laboratory based prognostic indices, severity status, clinical risk factors noted in Section 9.3 along with potential empirical model identified risk factors. These models will be run for the myocarditis cases and controls identified with ICD-10-CM codes in the EHR, and according to the inclusion and exclusion criteria as provided in Section 9.2, as well as for the cases that are validated by clinician reviews as myocarditis using the available Brighton Collaboration Criteria and information in medical record notes, as specified in Section 9.6. Model parameters will be detailed in the SAP.

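### The Cohort 1 infection exclusion ignores a positive SARS-CoV-2 test dated shortly after the myocarditis code, so a recently vaccinated patient with such a test stays a post-vaccine case

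*Protocol*

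**What the plan says.** Section 9.2.1 of the protocol (Myocarditis cases) defines the two pandemic-era cohorts by events dated before the diagnosis.

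- **Cohort 1, post-vaccine:** "Record of mRNA vaccination within 21 days prior to the myocarditis diagnosis", and the patient must be "without a record of SARS-CoV-2 positive test within 8 weeks prior to myocarditis diagnosis".
- **Cohort 2, post-infection:** "Record of SARS-CoV-2 positive test within 8 weeks prior to myocarditis diagnosis, with no record of mRNA COVID-19 vaccination during that time". Section 9.1 and the Abstract give the same direction: the code must fall "within 8 weeks after a positive SARS-CoV-2 test".
- **Cohort 3, pre-COVID:** "Most recent Myocarditis diagnosis date prior to 01 November 2019", so it cannot take in any pandemic-era case.

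Section 9.7 sets the index date as the "date of myocarditis diagnosis code for myocarditis cases". Section 9.1 adds: "Additional details on index dates and episode definitions will be provided in the SAP". Section 9.6 describes the note review as deciding whether each case is confirmed as myocarditis. It describes no step that moves a case from one cohort to another.

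**The concern.** The infection exclusion in Cohort 1 exists to keep infection-associated myocarditis out of the vaccine cohort. It does not do so when the first positive result is dated just after the code. One qualifying inpatient record is enough to make a case, so the code and the first test can fall in the same admission. The order of two administrative dates then decides how the patient is labelled.

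The primary objective compares risk factors across the cohorts, and Cohort 1 is the smallest of the three. Any infection-associated cases left in it pull its profile towards that of Cohort 2. The note review would not remove them, because a patient with real myocarditis and a concurrent infection is still confirmed as having myocarditis. Section 9.9 discusses infections that never reach the record, but not infections recorded shortly after the code.

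**Working it through.** **Cohort assignment.** Set the myocarditis code at day 0 and apply the section 9.2.1 rules: a vaccination window of 21 days for Cohort 1, and a test window and no-vaccination window of 8 weeks (56 days) for Cohort 2. The text does not say whether a same-day test counts as prior, so both readings are shown for day 0.

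| First positive test | Vaccinated day −10 | No vaccination |
|---|---|---|
| None | Cohort 1 | No cohort |
| Day −30 or −2 | No cohort | Cohort 2 |
| Day 0, same day counts as prior | No cohort | Cohort 2 |
| Day 0, same day does not count | Cohort 1 | No cohort |
| Day +1 or +3 | Cohort 1 | No cohort |

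The last row is the point, and it does not depend on how same-day tests are read. The day 0 rows show that the unstated same-day rule changes the assignment in both columns. A patient vaccinated on day −40 enters no cohort whatever the test date, so the direction of the test window makes no difference there.

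**Number affected.** The plan states no figure to reproduce. Section 9.5 gives about 240 myocarditis cases within 21 days of mRNA vaccination. The share first testing positive after the code is not given. Assuming 2–10%:

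- 0.02 × 240 = 4.8, about 5 cases
- 0.10 × 240 = 24 cases

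Section 9.5 does not say whether the infection exclusion or the note requirement had been applied to the 240, so the base is itself approximate.

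**Effect on an odds ratio (illustration; all inputs assumed).** Take a factor with 20% prevalence, a true OR of 1 in vaccine cases, and an OR of 2 or 3 in infection cases. Prevalence in infection cases is p1 = OR × 0.2 / (0.8 + OR × 0.2), which gives 0.333 or 0.429. With contamination m, prevalence in Cohort 1 is p = (1 − m) × 0.2 + m × p1, and the observed OR is [p/(1 − p)] / 0.25.

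- m = 0.02, OR 2: p = 0.2027, observed OR 1.02
- m = 0.10, OR 3: p = 0.2229, observed OR 1.15

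For comparison, consider sampling error from 240 cases at 20% prevalence (48 with the factor, 192 without), ignoring the controls' contribution. SE(log OR) = √(1/48 + 1/192) = 0.161, so the 95% limits lie a factor of exp(1.96 × 0.161) = 1.37 either side.

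**The case against.** Requiring the infection to be recorded before the outcome is a defensible definition of a post-infection cohort. Counting later tests uses post-index information and brings in incidental or hospital-acquired positives. That argument stands for Cohort 2. It has less force for Cohort 1, where the test serves only to exclude and the price is a few cases.

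The SAP may settle how the episode is dated and how same-day tests are treated, and that could shrink the problem. Section 9.9 also expects delayed diagnosis, which makes a test before the code more likely. Both are fair. Even so, the direction of the window is fixed in the inclusion criteria, and extending it past the diagnosis would change section 9.2.1.

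Notes from thirty days either side of index are available to the clinicians, so an in-admission positive may be visible to them. This mitigates little, because no instruction tells them to act on it.

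A reader might infer three stronger things that the documents do not support:

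- **That every positive test during the index admission is missed.** A test dated before the code counts even if it belongs to the same admission.
- **That Cohort 2 loses a large, calculable number of cases.** No share is given, and section 9.5 does not show that its 1,730 cases are those left after this rule.
- **That testing behaviour will therefore appear as a risk factor.** This is possible, but the protocol plans controls with similar database activity and lists prior healthcare use as a variable.

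**Conclusion.** The gap in Cohort 1 is real on the protocol's wording. A recently vaccinated patient whose first positive test is dated shortly after the code remains a post-vaccine case, and nothing later corrects the label. The counterpart without a recent dose falls outside all three cohorts.

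Its size is unknown. About 5–24 of roughly 240 cases is what an assumed 2–10% would give. Under the further assumptions in the illustration, the shift in a Cohort 1 odds ratio (to about 1.02–1.15 from a true 1) is smaller than sampling error. The point therefore rests on the purpose of the exclusion and the low cost of repairing it, not on a demonstrated large bias. It is a worthwhile, cheap improvement and not a must-fix.

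**What to change.** In section 9.2.1:

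1. Extend the Cohort 1 exclusion to positive tests from 8 weeks before the index date through the index encounter, with a short stated post-index cap. Seven days is offered as an example and does not come from the documents.
2. State, for both cohorts, that a test dated on the index day counts.
3. Keep the primary Cohort 2 definition as test before diagnosis.
4. Report how many patients have their first positive in the post-index window. Where feasible, add those who meet the Cohort 2 vaccination condition to Cohort 2 in a sensitivity analysis based on the code-defined cases.
5. Run Cohort 1 with the protocol's current backward-only window as a sensitivity analysis.

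**Cost.** The Cohort 1 change needs only structured data already held. It loses a few cases whose positives are incidental or hospital-acquired, and item 5 shows the effect. Changing the primary Cohort 2 definition would cost more: two-clinician note review, a data collection form for each adjudicated patient, and matched controls. The amendment history already records delays in adjudication and control construction. Limiting item 4 to code-defined cases avoids the review work, though the added cases would still need matched controls.
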